All patients will undergo a LGE-MRI within 30 days prior to the ablation procedure. The clinical purpose of the initial MRI is to define the anatomy of the heart chambers as well as the vessels for procedure planning. For research purposes, we will use this initial clinical MRI to delineate atrial structural remodeling or fibrosis to be used during the procedure in patients randomized to group 2 (pulmonary vein isolation + scar-based ablation) and for later analysis in all patients.

Imaging is done at our institution and will be reviewed for quality by the study staff. LGE-MRI sequences that do not meet quality standards for fibrosis analysis will not be further processed and these patients will be excluded from the study. Subjects for whom images are successfully evaluated will be randomized to the study groups.

This will be followed by block randomization in 1:1:1 format to a) pulmonary vein isolation (PVI) only (current standard of care), b) PVI plus targeting of dense LGE sites, which are confirmed on bipolar mapping to have voltage <0.1 mV, and c) PVI plus targeting of rotor anchor sites predicted by modeling.

At baseline, all patients will be evaluated for their quality of life (QOL) using the Short-form health survey (SF-36) (Ware & Sherbourne, 1992) for overall as well as AF-related impact on quality of life (Refer to additional study documents). The severity of symptoms will be tested using the European Heart Rhythm Association (EHRA) score of atrial fibrillation and the Canadian Cardiovascular Society (the CCS-SAF) scale (Dorian et al., 2006). Clinical data will be stored electronically and linked to a specific research ID number. Information linking de-identified data to the patients will be stored in the locked research office, in a password-protected file. Only members of the research team, in charge of collecting clinical information, will have access to this file. Individual subject binders containing signed consent forms and clinical source documentation will be labeled using study subject numbers and stored in the locked research office mentioned previously.

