A pre-ablation cardiac MRI is clinically indicated to assess baseline cardiac anatomy prior to procedure. Routine and LGE protocols will be used to acquire MR images. All patients will be asked to undergo a repeat LGE-MRI 12 months after the ablation. This is done for research purposes. Renal function is routinely monitored prior to gadolinium-enhanced MRI as a standard of clinical care.

With regards to the ablation procedure, all patients will undergo AF ablation. The procedure consists of circumferential pulmonary vein lesions under electro-anatomical guidance using CARTO (Biosense Webster Inc., Diamond Bar, CA). Operators will use either a 3.5mm irrigated tip radiofrequency ablation catheter (ThermoCool SmartTouch, Biosense Webster Inc., Diamond Bar, CA) or a cryoballoon catheter (Arctic Front Advance, Medtronic Inc., Minneapolis, MN). This procedure is FDA approved and will be conducted in all treatment arms according to standard of care. However, patients in the second group will undergo additional targeting of dense LGE sites, confirmed on bipolar mapping to have voltage <0.1 mV and patients in the third group will undergo targeting of rotor anchor sites as predicted by computational modeling. A detailed protocol of rotor ablation is described in the literature and shows no added complications compared to the conventional procedure (Narayan et al., 2014).

To prevent short-term recurrence of AF, patients will be kept on anti-arrhythmic regimen for the first 1 to 3 months after the ablation to be discontinued thereafter in the absence of AF recurrence, at the discretion of the treating physician. In addition, standard protocols for anticoagulation prior to, during, and after the ablation procedure will be applied.

After the ablation, clinical follow-up visits are scheduled at 3, 6 and 12 months. Research follow-up questionnaires and 12-lead ECG recordings will be done at the same day of the visits. All patients will undergo rhythm monitoring to detect AF recurrence using a portable, smartphone operated, AliveCor® Mobile ECG device. The AliveCor® Mobile ECG is a mobile, clinical-quality electrocardiogram (ECG) recorder. The software application can store thousands of recordings on smartphones or tablets and these recordings are wirelessly transmitted to AliveCor, Inc. (AliveCor) servers accessible to authorized users including healthcare providers. This device will be provided to the patients at no cost after enrollment in the study.

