Prior to ablation, patients will be asked to complete 7 days of twice-daily 1-minute rhythm monitoring using the AliveCor® device. After the procedure, follow-up will be done on a weekly basis through trans-telephonic transmissions of ECG recordings. Periodic reminders will be sent to patients (via telephone, email, or mail) regarding follow up transmissions in the event that a weekly transmission is missed. Although preferred, it is not imperative that all patients complete all weekly follow up transmissions. In addition, study participants will be advised to provide recordings if they experience heart-related symptoms (palpitations, shortness of breath, rapid heartbeat, chest pain). This extensive rhythm monitoring protocol is not standard of care and is done for research purposes. Review of the rhythm monitoring data will be performed in accordance with current clinical guidelines. The device software and the investigators will analyze rhythm strips and a report will be available to the research team and to the treating physician upon his/her request.

In addition, upon detection of any arrhythmia with important clinical implications, the investigators will notify the electrophysiologist involved in the care of the patient. The research team may contact the patient directly if prompt action is advised, such as reporting to the local emergency room or following up with their electrophysiologist. The rhythm monitoring protocol utilized in this study may result in unscheduled visits to the physician. If a repeat ablation procedure is indicated, it will be scheduled according to standards of clinical care.

A detailed study timeline is attached at the end of the document.

b. Study duration and visits.

We aim to complete the proposed study protocol in two years. After the ablation, patients will be followed at 3, 6 and 12 months via in clinic visit; a 1 month and 9 month follow up will take place via remote ECG transmission. Follow-up research questionnaires and post-ablation MRI will be scheduled to coincide with the routine clinical visits. Hence, no additional visits will be required of research participants unless it was not possible to schedule the MRI on the same day as clinic visits. Only then will we ask participants to present to JHH for the follow-up MRI.

c. Blinding, including justification for blinding or not blinding the trial, if applicable.

N/A

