Patients undergoing MRI angiogram are routinely injected with gadolinium as contrast. Gadolinium-based MRI contrast agents are used to visualize scar/ablation lesions in the atrial wall (McGann et al., 2014). Gadolinium chelates used as intravenous contrast media are extremely safe in patients with normal kidney function and do not exhibit the nephrotoxicity associated with iodinated media. Minor reactions including nausea and hives may occur in a small percentage of cases. Severe anaphylactic reactions are extremely uncommon (Runge, 2001).

- b. Justification and safety information if FDA approved drugs will be administered for non-FDA approved indications or if doses or routes of administration or participant populations are changed.

Gadolinium (total dose of 0.2 mmol/kg) will be administered 10 minutes prior to delayed enhancement imaging to evaluate for the presence of myocardial scar. Gadolinium-based contrast agents are not FDA-approved for diagnosis of cardiac disease by MRI. However, these agents have been routinely used for more than 10 years at the JHH and other centers for clinical and research purposes to evaluate diseases of the myocardium and vessels (Akoum & Marrouche, 2014) (Zareian et al., 2015). The standard gadolinium dose at JHH and other institutions in cardiac MRIs is a maximum of 0.2 mmol/kg.

- c. Justification and safety information if non-FDA approved drugs without an IND will be administered. N/A

7. Study Statistics

- a. Primary outcome variable.

Data from AliveCor® Mobile ECG rhythm device recordings, follow-up visits (examinations and ECGs), and QOL/follow-up questionnaires will be used to identify the success rates of the procedure. Procedure failure is defined as symptomatic or asymptomatic AF/Atrial flutter/Atrial tachycardia of at least 30 seconds duration that is documented by an ECG or device recording system, occurring after the 3-month blanking period following catheter ablation. Individually tailored ablation strategies for suppression of persistent AF have not been investigated. We hypothesize that individually tailored ablation strategies will improve AF/AT suppression compared to PVI alone. The association of time to AF/AT recurrence with ablation strategy will be examined in 30 randomized patients.

- b. Secondary outcome variables.

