Comparison variables will be presented as means \pm SD, and categorical variables as numbers and percentages. Differences between treatment groups will be assessed using the Pearson Chi-square test and the Wilcoxon rank-sum test. Survival curves for time to event analysis will be estimated using the Kaplan-Meier method, and the differences between the curves will be tested for significance with the log-rank statistic. Weekly event rates will be calculated by dividing the event rate by the maximum follow-up period in each arm of the Kaplan-Meier analysis. Hazard ratios will be calculated by univariate and multivariate analysis using the Cox proportional-hazards regression model. When comparing MR image characteristics as well as LA function between pre and post-ablation imaging, the Student's t-test will be using for comparison of the means. All statistical testing will be 2-tailed. Results will be considered statistically significant at a level of $p < 0.05$.

- d. Early stopping rules. N/A

8. Risks

- a. Medical risks, listing all procedures, their major and minor risks and expected frequency.

As discussed above, all procedures except the post-ablation MRI is part of the standard clinical care. In addition, groups reporting their experience with substrate-based ablation have not encountered increased complications compared to the conventional ablation procedure (Narayan et al., 2012). In addition, there is no data suggesting any health hazard associated with magnetic field exposure (Schenck, 2000). All patients with pacemakers, implanted defibrillators or electronic/metallic devices, shrapnel and other metals such as metal in the eyes will be excluded.

Gadolinium chelates used as intravenous contrast media in MRI are considered safe and do not exhibit the nephrotoxicity associated with iodinated media. The injection of contrast intravenously is not painful, but

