may cause discomfort, tingling or warmth in the lips, metallic taste in the mouth, tingling in the arm, nausea, or headache. These symptoms occur in less than 1% of people and are short-lived. Allergic reactions to contrast are extremely rare and the risk of a severe reaction is less than 1 in 300,000. Recently, gadolinium-based contrast has been reported to cause Nephrogenic Systemic Fibrosis (NSF) in patients on dialysis or renal failure. The FDA has issued warnings with regards to this issue ((FDA), 2010). Hence, patients with renal failure and those on dialysis will be excluded from our study.

- b. Steps taken to minimize the risks.

Patients will be monitored for acute symptoms of hypersensitivity after contrast administration including hives, flushing, and nausea. Patients with acute or chronic renal insufficiency (GFR <30ml/min/1.73m²), or patients in the perioperative liver transplantation period are at risk of developing NSF. To minimize the risks, such patients will be excluded from the study.

All standard pre-procedure activities i.e. pregnancy testing and renal function testing will be conducted by JHH staff according to standard institutional protocol.

- c. Plan for reporting unanticipated problems or study deviations.

The study team will maintain reporting in accordance with the JH IRB's AE and SAE reporting criteria.

- d. Legal risks such as the risks that would be associated with breach of confidentiality. N/A

- e. Financial risks to the participants.

All MRIs performed post-ablation will be provided at no cost if not indicated clinically. The AliveCor® Mobile ECG devices will also be provided at no cost. All other tests and follow-up visits are part of routine clinical care and will be billed to insurance.

9. Benefits

- a. Description of the probable benefits for the participant and for society.

Patients enrolling in this study may not experience direct benefit from this study. However, the results of the study may benefit those with atrial fibrillation. The SIMPLE-AF study aims to improve the efficacy, safety and outcomes of the ablation procedure for persistent AF. By improving the rate of AF recurrence, we will also reduce the overall economic burden of AF. Potential long-term side effects of the procedures at hand will be investigated, as well as ways to avoid it.

10. Payment and Remuneration

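### Section 8a calls everything except the post-ablation MRI standard care, contrary to section 4a, and no complication or adverse event outcome is defined or compared by arm

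*Combined protocol and SAP*

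**What the plan says.** **Risk section.** Section 8a opens, referring back to the earlier text, with the statement that "all procedures except the post-ablation MRI is part of the standard clinical care". Its next sentence says that groups using substrate-based ablation have not met more complications than with the conventional procedure, and cites a 2012 rotor-ablation trial.

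**Study design.** Section 4a describes the first arm as "pulmonary vein isolation (PVI) only (current standard of care". It says the PVI procedure follows standard of care in every arm, and then sets two arms apart: "patients in the second group will undergo additional targeting of dense LGE sites", and "patients in the third group will undergo targeting of rotor anchor sites as predicted by computational modeling". Of published rotor ablation it says that the literature "shows no added complications compared to the conventional procedure". Of the follow-up recordings it says: "This extensive rhythm monitoring protocol is not standard of care and is done for research purposes".

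**Outcomes.** Section 7a has AF/AT recurrence as the primary outcome and remarks: "Individually tailored ablation strategies for suppression of persistent AF have not been investigated". Section 7b has imaging outcomes, including the change in left atrial and left ventricular strain by ablation strategy. Section 7c contains no safety analysis, and 7d answers early stopping rules with N/A.

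**Safety aims.** Section 9a names safety among the things the study aims to improve and adds: "Potential long-term side effects of the procedures at hand will be investigated". Section 8c handles adverse events only through IRB reporting. The timetable in Appendix A has no adverse event row.

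**The concern.** Section 8a is where the IRB and participants learn which risks come from the research and which would be run anyway. If it assigns everything but one MRI to routine care, the extra ablation given because of randomisation is not identified as a research risk, and neither is the extra monitoring.

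The second issue is whether the trial can deliver what section 9a promises. Adding lesions to PVI is the experimental step, and procedural complications are the obvious harm to count. With no defined event outcome, no common time window and no comparison by arm, any safety statement at the end would rest on whatever happened to be reported, summarised in a way chosen after the data are seen.

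**Working it through.** The plan gives no complication rate and no safety sample size, so there is no figure of its own to reproduce. The check is mainly a comparison of texts.

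**Step 1. Is the 8a statement consistent with the rest?**

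| Component | Section 8a | Elsewhere | Consistent? |
|---|---|---|---|
| Post-ablation MRI | Research | 4a: research | Yes |
| Rhythm monitoring | Standard care, by implication | 4a: explicitly not standard of care | No |
| PVI | Standard care | 4a: standard of care in all arms | Yes |
| Added dense-LGE targets (group 2) | Standard care, by implication | 4a: an addition to the arm labelled standard of care | No |
| Added model-predicted rotor targets (group 3) | Standard care, by implication | 4a: as for group 2 | No |

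The monitoring row alone makes the sentence untrue. The added ablation is the more important mismatch.

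**Step 2. How many patients?** The inputs are 30 patients (sections 1 and 4a) and 1:1:1 block randomisation (4a). 30 / 3 = 10 per arm, so groups 2 and 3 together have about 10 + 10 = 20 of 30, or two thirds.

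**Step 3. Does the rest of 8a fill the gap?** Its heading asks for each procedure with its risks and their expected frequency. Contrast reactions get frequencies (under 1% for minor symptoms, under 1 in 300,000 for severe reactions). Ablation gets none in any arm. The one reassurance rests on published rotor ablation. Section 1 describes that technique as mapping by wide sampling of the atria during AF, whereas group 3 uses sites predicted by computational modelling and group 2 uses dense LGE with low voltage. Neither 8a nor the procedure text in 4a cites a complication source specific to those two targeting methods.

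**Step 4. Which outcomes are compared by arm?** AF/AT recurrence (7a), and strain change from baseline to 1 year (7b, matching a secondary objective in section 2). Complication or adverse event outcomes compared by arm: none.

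**Step 5. What could a by-arm event table show?** This is context only. For 0 events in n patients, the exact two-sided 95% upper limit is 1 − 0.025^(1/n).

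- n = 10: 1 − 0.025^(1/10) = 1 − 0.6915 = 30.8%
- n = 20: 1 − 0.025^(1/20) = 1 − 0.8316 = 16.8%

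With one-sided 95% limits (0.05 in place of 0.025), these become 25.9% and 13.9%.

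The chance of seeing at least one event is 1 − (1 − p)^n. The true rates p below are assumptions; the documents give none.

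| Assumed p | n = 10 | n = 20 |
|---|---|---|
| 2% | 18% | 33% |
| 5% | 40% | 64% |
| 10% | 65% | 88% |

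A table at this size describes what happened. It is not a test of a difference.

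**The case against.** Five points can fairly be made for the plan.

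1. **Harm is not ignored.** A reader might infer that no safety outcome at all is compared by arm. The documents do not support that. Section 7b recognises that more extensive ablation may impair left atrial function and examines strain change by ablation strategy, which goes some way towards the long-term side effects promised in 9a. This stands, and it limits the point to complications and adverse events, which strain does not capture.

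2. **The added ablation is not left out of 8a.** The sentence after the disputed one addresses substrate-based ablation and compares it with the conventional procedure. This stands too. The fault is the wrong label and the absence of risks and frequencies, not silence.

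3. **Reporting no added complications does not contradict saying that tailored strategies are uninvestigated.** The first statement, in 4a, concerns published rotor ablation. The second, in 7a, introduces an efficacy hypothesis. Both can be true. What remains is a doubt about carrying published experience over to these targets.

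4. **The upper limits answer a claim the plan does not make.** The reassurance is drawn from the literature, not inferred from these 30 patients. Agreed: the limits indicate only what the proposed table can and cannot show.

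5. **The larger trial is a separate matter.** A reader might infer that the planned 300-patient trial would go ahead without a comparison of complications. Sections 1 and 11 give no outcomes for that trial, so nothing can be said about it.

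None of this rescues the 8a sentence or supplies an adverse event outcome.

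**Conclusion.** The concern holds in two parts of different strength.

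The contradiction is firm. The blanket statement in 8a cannot stand beside 4a on the rhythm monitoring, which all patients use, or on the added ablation in about 20 of 30. The count assumes that 30 patients are randomised and that the 1:1:1 ratio is met.

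The safety gap is real but narrower than a complete absence of safety outcomes. The study names safety as an aim, yet it neither defines nor compares by arm any complication or adverse event. Whether published experience carries over to dense-LGE or model-predicted sites is an open question on these documents; they do not show that the added ablation is more hazardous.

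The change should be made. It corrects an inaccurate risk statement and gives the stated safety aim a planned, if only descriptive, output.

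**What to change.** 1. **Section 8a.** Name the rhythm monitoring and the added ablation in groups 2 and 3 as research procedures alongside the post-ablation MRI. List their risks, with expected frequencies where a source exists, and say where experience comes from a different targeting method. Reconcile the text with 4a.
2. **Section 8e.** Check in the same edit the sentence that treats all other tests and visits as routine care, since 4a accepts that the research monitoring may lead to unscheduled visits.
3. **Section 7b.** Add a descriptive secondary outcome: procedure-related adverse events and serious adverse events to 12 months, by arm and for tailored (about 20) versus PVI only (about 10), as patient counts with exact 95% confidence intervals. State that no formal test is planned and that zero events will not be read as evidence of no added risk.
4. **Appendix A.** Add an adverse event row at the existing contacts.

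The cost is protocol and risk wording plus one table. A short uniform event form at the existing visits may also be needed. Section 8c refers to IRB criteria that the documents do not reproduce, so it cannot be assumed that current reporting would capture every relevant event through 12 months. Sample size, arms and visit schedule do not change.

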APPENDIX

A. STUDY PROTOCOL TIMETABLE

	Screening/ Pre-Ablation	Ablation	1-Month Follow-up	3-Month Follow-up	6-Month Follow-up	9-Month Follow-up	12-Month Follow-Up
Informed Consent	X						
History and Physical Exam	X			X	X		X
12-Lead ECG	X			X	X		X
Echocardiography	X (As indicated)						
AliveCor® Rhythm Monitoring	X		X	X	X	X	X
LGE-MRI	X						X
Follow-up Questionnaire	X			X	X		X
